- Arm 1: Treatment as Usual (TAU) control: A “usual care” control group (e.g., antidepressants, watchful waiting, psychosocial therapy, or no treatment, all determined by the participant in consultation with their TAU providers). All TAU will be recorded for all participants in all study conditions; or
- Arm 2: TAU + Minimal BLT Encouragement: TAU plus two minimal communications (mailed letter, secure EHR message, email, or text) identifying BLT as a promising treatment and outlining steps for participants to self-initiate. Arm 2 will not include any phone coaching or adherence promotion.
- Arm 3: TAU + Enhanced BLT Encouragement + Adherence Promotion + MI: TAU plus 2-6 brief calls to encourage BLT use, advise on purchase of a light box (LB) that meets all ideal technical

standards, assist with obtaining compensation for LB purchase, educate for correct LB use, and provide motivational interviewing (MI) as needed to promote adherence.

Outcomes will be assessed at baseline, 2, 4, and 6 months. The acute intervention period will be for 2 months. The primary outcome will be scores on the Patient Health Questionnaire-9 (PHQ-9), selected as representative of how depression is assessed in many usual care settings, consistent with effectiveness research principles.

5. Study Population

a. Number of Subjects

We will enroll 90 to 100 participants.

b. Inclusion and Exclusion Criteria

Potentially eligible individuals will be screened at two points in the recruitment phase: 1) preliminary identification of likely participants via a search of KPNW electronic health record (EHR) and 2) phone or online screening survey.

EHR inclusion criteria:

- Age 18-69 years, inclusive, and
- New episode of unipolar depression within the last month, defined as: New ICD-10 diagnosis of SAD or unipolar depression (i.e., major depression, minor depression, depression not otherwise specified, and/or adjustment disorder with depressed mood) AND usual care administration of the PHQ-9 depression scale in the last 30 days, with a total score of 10 or higher, and
- Participant must have a kp.org MyChart account, with evidence of use in the last 12 months.

EHR exclusion criteria:

- Chronic depression: ICD-10 diagnosis of SAD or unipolar depression in the 6 months prior to case-identification;
- Elevated PHQ-9 (score of 10 or higher) in the 6 months prior to case identification.

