We will conduct exploratory analyses of the BLT mediation pathway as the extent to which the relation between BLT and outcomes is mediated by changes in participants' 1) sleep (SASS-Y and actigraphy, and PSQI subjective sleep quality), 2) total physical activity, and 3) circadian timing and chronotype. For example, to evaluate the mediating effect of PSQI sleep quality we will regress post-acute treatment PSQI on baseline PSQI and a randomization condition indicator; and we will regress follow-up PHQ-9 at post-acute treatment PSQI and a randomization condition indicator. Using the product coefficients mediation approach, we will use the resulting regression coefficients and standard errors (SEs) to estimate the indirect effect. Because SEs of the products of regression coefficients are not normal, we will use bias-corrected bootstrapping to estimate the SEs for the indirect effect. We will use a similar approach for the MI pathway to test the mediating effect of participants' increased readiness to change on BLT adherence.

Analysis of secondary outcomes. Continuous measures over time will be modeled with HLM methods described above. Health service use can be categorized into binary (e.g., met threshold for medication possession ratio, had > 1 hospitalization) and count outcomes (e.g., N of ED visits, primary care visits). Binary outcomes will be modeled with multivariable logistic regression, and the coefficient of study arm membership (e.g, 0=TAU, 1=TAU+BLT+AP & TAU+BLT) is the coefficient of primary interest. Count outcomes are modeled with either multivariable Poisson or negative binomial regression depending on which yields optional fit.

BLT process outcomes. To examine the effects of adherence and MI elements, we will contrast Arms 2 vs. 3 across months 2, 4, and 6, comparing: (a) % cumulative light box purchase; (b) % cumulative compensation for light box purchase; and (c) mean EMA-adherence (aka, dose). We will conduct these analyses using methods similar to those for secondary outcomes; however, the analysis sample will be restricted to Arms 2 and 3. We will describe similar metrics in the TAU condition (Arm 1).

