allows). Meta-analyses suggest an overall effect size for BLT of $d=0.84$. We conservatively estimate the effect size likely to be obtained in this pilot trial as lower than reported in meta-analyses because this is a real-world effectiveness population; even with Arm 3 adherence promotion BLT adherence is likely to be lower than in efficacy trials, leading to lower clinical benefit. Assuming a retained sample size of $N=81$ at the final 6-month assessment, we conducted power analysis for the HLM of the primary outcome (using SAS version 9.4) to determine the minimum detectable effect size. At a two-tailed alpha level of 0.05 and conservatively assuming an autocorrelation of 0.70, we would have 80% power to detect a Cohen's d for the time by arm effect as small as 0.39 for the contrast between active intervention arms (Arms 2 and 3) and TAU, and as small as 0.55 for contrasts between individual arms; both estimates are medium effects. This pilot study is not powered to evaluate mediation, but we will conduct mediation analyses as if this were the full-powered R01 confirmatory trial to test feasibility of the analytic methods and to provide informative estimates of potential mediators. We estimate that we will have 80% power using a 95% bias-corrected confidence interval to identify effect sizes of 0.43 or larger for the pathways between randomization status to mediator, and mediator to outcome (BLT adherence for MI pathway, and PHQ-9 for BLT pathway); and we will be able to identify direct and indirect effects of 0.19 or larger, which correspond to a small-medium effect.

Use of pilot results to estimate power for the future full trial. Regardless of the between-condition effect size that we observe in this pilot, we will heed the cautions that have been raised about using pilot study results to estimate effect for full trial power/sample calculations. We will consider between-condition effect size (ES) results highly tentative given the small pilot sample and will use it only with wide confidence intervals when employing it to estimate power for the future full pragmatic trial. For example, if we obtain an effect size of $d=0.45$, we will generate a power/sample size matrix with estimated effects of 0.35, 0.40, 0.45, 0.50—all ranging around the observed effect from this pilot, but trending to somewhat smaller and more conservative effects.

b. Sharing of Results with Subjects

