## Moderation and mediation

In addition to primary outcome analyses we will conduct exploratory analyses of moderation using variables identified through previous research and clinical expertise, specifically indication of pharmacotherapy use (1=yes, 0=no), age (continuous), gender (1=female, 0=male), race and ethnicity (1=racial/ethnic minority, 0=non-Hispanic white), baseline PHQ-9 (1=clinically elevated, 0=below clinical range), and EHR indication of mental health comorbidities such as eating disorders, anxiety (1=comorbidity, 0=no comorbidity). Moderation will be indicated by a significant time x arm x moderator interaction in HLM.

We propose to conduct exploratory analyses of the BLT mediation pathway as the extent to which the relation between BLT and outcomes is mediated by changes in participants' 1) sleep (sleep diary and actigraphy, and ISI subjective sleep quality), 2) total physical activity, and 3) circadian timing and chronotype. For example, to evaluate the mediating effect of ISI sleep quality we will regress post-acute treatment ISI on baseline ISI and a randomization condition indicator; and we will regress follow-up PHQ-9 at post-acute treatment ISI and a randomization condition indicator. Using the product coefficients mediation approach, we will use the resulting regression coefficients and standard errors (SEs) to estimate the indirect effect[10-12]. Because SEs of the products of regression coefficients are not normal, we will use bias-corrected bootstrapping to estimate the SEs for the indirect effect.[12] We will use a similar approach for the MI pathway to test the mediating effect of participants' increased readiness to change on BLT adherence.

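### The sleep mediators are tested only against the PHQ-9 total, so if the form carries the standard sleep item, part of any indirect effect through sleep may be item overlap

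*Protocol*

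**What the plan says.** The Protocol, Section 6.a, lists the mediators on the BLT pathway as "1) sleep (SASS-Y and actigraphy, and PSQI subjective sleep quality), 2) total physical activity, and 3) circadian timing and chronotype". The SAP (Moderation and mediation) lists "sleep (sleep diary and actigraphy, and ISI subjective sleep quality" for sleep, so the two documents name different self-report sleep measures but share actigraphy.

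The worked example has the same structure in both. For the arm-to-mediator path, the Protocol says "we will regress post-acute treatment PSQI on baseline PSQI and a randomization condition indicator". For the mediator-to-outcome path it says "we will regress follow-up PHQ-9 at post-acute treatment PSQI and a randomization condition indicator", and the SAP says "we will regress follow-up PHQ-9 at post-acute treatment ISI and a randomization condition indicator". I read the word before the sleep score as *on*. That second model contains the post-treatment sleep score and arm, but not baseline PHQ-9. The indirect effect is the product of the two coefficients, with bias-corrected bootstrapping.

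The Protocol's power section confirms the outcome for each pathway: "mediator to outcome (BLT adherence for MI pathway, and PHQ-9 for BLT pathway". It takes 0.43 as the detectable size for each path and adds "we will be able to identify direct and indirect effects of 0.19 or larger". Neither document defines a reduced PHQ-9 score or a sensitivity analysis for item content.

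Both documents call the mediation analysis exploratory, and the Protocol says the pilot is not powered for it. The Protocol nevertheless intends to run it as the later confirmatory trial would, both to rehearse the method and to obtain useful estimates of the mediators.

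**The concern.** The secondary objective asks whether improved sleep carries the effect of BLT on depression. If one of the nine PHQ-9 items asks about sleep, the mediator and part of the outcome measure the same symptom. A treatment that improves sleep then lowers the total through that item even when the other eight symptoms do not move. The product of coefficients cannot tell this apart from better sleep lifting mood. Baseline adjustment does not help, because the overlap lies in the follow-up scores.

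At stake is how the sleep result is read, and whether the full trial inherits a mediation model with the same ambiguity. The primary PHQ-9 comparison is not affected.

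**Working it through.** **Inputs from the documents.** Path size 0.43, detectable indirect effect 0.19 and retained N=81 (Protocol, Power analysis, sample size). Allocation 1:1:1, hence 27 vs 54 for the pooled contrast. The SAP's abbreviation list describes the PHQ-9 as the nine-item version.

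**Assumptions, not in the documents.** One of the nine items is a sleep item. Month-2 PHQ-9 SD is 5 to 6 and item SD is 0.9 to 1.1. The item correlates 0.5 to 0.8 with a self-report sleep score. To isolate overlap, sleep is taken as unrelated to the other eight items.

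**The plan's figure.** 0.43 × 0.43 = 0.185. This matches 0.19 within rounding of the paths (0.435² = 0.189). The 80% power could not be reproduced exactly, because the documents give neither the N nor the scale for it. A bias-corrected bootstrap simulation gave about 95% at N=81 and 83% at 27 vs 27 with standardised paths, and about 53% at N=81 with the first path read as Cohen's d.

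**Overlap alone, standardised.**
- Mediator-to-outcome path from the item: b = r × SD(item) / SD(PHQ-9).
- Low end: 0.5 × 0.9 / 6 = 0.075. High end: 0.8 × 1.1 / 5 = 0.176.
- Indirect effect: 0.43 × 0.075 = 0.032, to 0.43 × 0.176 = 0.076.
- Share of the benchmark: 0.032 / 0.185 = 17%, to 0.076 / 0.185 = 41%.

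The share equals b / 0.43, so it does not depend on the scale of the arm-to-mediator path. It is proportional to r: a mediator with half the correlation has half the overlap. Actigraphy, a device measure, may therefore contribute less.

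**Simulation of the two planned regressions.** BLT shifts sleep only, by d = 0.3 to 0.8. Item SD is 1, item-to-sleep correlation is 0.5 or 0.7, the SD of the other eight items is 4.5, and baseline and follow-up sleep correlate 0.6. There were 300 trials per setting with 500 resamples, so the detection rates have standard errors of up to about 3 percentage points. Effects are in PHQ-9 points; negative means improvement.

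| Setting | Full PHQ-9: indirect effect | CI excludes 0 | Eight items: indirect effect | CI excludes 0 |
|---|---|---|---|---|
| N=81, d 0.3–0.8, eight items unrelated to sleep | −0.14 to −0.57 | 10–38% | −0.03 to +0.03 | 5–9% |
| N=81, d 0.43, unrelated | −0.22 to −0.32 | 18–28% | −0.01 to −0.03 | 5–7% |
| N=400 (illustrative), d 0.43, unrelated | −0.23 to −0.30 | 67–86% | −0.01 to 0.00 | 4–6% |
| N=81, d 0.3–0.8, eight items correlate 0.2–0.4 with sleep through a common cause | −0.41 to −1.99 | 37–99% | −0.27 to −1.43 | 21–97% |

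Between N=81 and N=400 the overlap effect stays about the same size, while the chance of declaring it significant rises.

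In the last row at d = 0.43, overlap supplies between (1.01 − 0.79) / 1.01 = 22% and (0.66 − 0.37) / 0.66 = 44% of the indirect effect on the total. The rest is confounding of the mediator-to-outcome path, and it remains after the item is removed.

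**The case against.** **The item content is not in the documents.** This is true. The Protocol also allows measures to be used in part. The point is conditional, and the sponsor can settle it from its own form.

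**The estimate is not wrong for the outcome named.** If BLT improves sleep and so lowers the PHQ-9 total, that effect does run through sleep. This stands. The bias is relative to the question of interest, which is whether sleep mediates depression beyond the sleep symptom. The eight-item result is therefore an addition to the planned analysis, not a replacement for it.

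**The analysis is exploratory and underpowered.** Also true, and no stated decision depends on it. But low power concerns precision, whereas overlap is systematic, and the Protocol means this analysis to rehearse the full trial's method.

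**A reader might infer more than the material supports.**
- That sleep will appear to mediate even if BLT changes nothing else. The artefact needs a real effect on sleep and comes from one item in nine. Alone, it gave a confidence interval excluding zero in only 10–38% of simulated trials at N=81.
- That removing the item leaves a clean mediation result. The last row of the table shows otherwise.
- That the sleep estimate will size the full trial. The section on using pilot results for future power concerns the between-condition effect size only.

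**Conclusion.** The point holds in a limited form. Both documents test the sleep mediators against the PHQ-9 total, with no analysis that separates item overlap from change in the other symptoms. If the form has its standard sleep item, overlap alone contributes a standardised indirect effect of about 0.03 to 0.08 for self-report sleep scores, or 17% to 41% of the plan's benchmark. That size rests on the assumed SDs and correlations and may be smaller for actigraphy.

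This would usually not be significant on its own in the pilot. It is worth correcting because sample size does not reduce it and the remedy is cheap. It has no bearing on the primary analysis.

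**What to change.** In the Moderation and mediation sections of the Protocol and the SAP, add three statements for the sleep mediators:

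1. The indirect effect will be reported on the PHQ-9 without its sleep item (eight items), beside the full PHQ-9 version.
2. Sleep will be read as mediating depression beyond the sleep symptom only if the eight-item result supports it.
3. The primary PHQ-9 outcome is unchanged.

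First confirm the item on the administered form. Apply the rule to whichever sleep measures remain once the Protocol and SAP lists are reconciled.

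The cost is SAP wording and one derived score from item responses to a scale already administered. The downsides are a less familiar score and a smaller estimated indirect effect. The write-up should say that this removes item overlap only. Confounding of the mediator-to-outcome path, whose model omits baseline PHQ-9, is a separate issue and needs its own treatment.

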Demographics data will be collected on all potential participants during the screening process and/or baseline assessment and will include race, ethnicity, sex assigned at birth, gender identity, relationship status, employment status, and education and income information.

Survey Measures

All measures will be administered at the baseline assessment and all follow-up assessments unless otherwise indicated. The surveys will include questions from the following measures, either in part or in their entirety: **Patient Health Questionnaire-9 (PHQ-9); Seasonal Pattern Assessment Questionnaire (SPAQ); Quick Inventory of Depressive Symptomatology, self-report (QIDS-SR); Geriatric Depression Scale (GDS);** the abbreviated **self-report Columbia Suicide Severity Rating Scale (C-SSRS); Altman Self-Rating Mania Scale (ASRM); Generalized Anxiety Disorder-7 (GAD-7); Brief Medication Questionnaire (BMQ); Short Form 6 Dimension (SF-6D); Pittsburgh Sleep Quality Index (PSQI); Reduced Version of the Morningness-Eveningness Questionnaire (rMEQ); Split Week Self-Assessment of Sleep Survey (SASS-Y); Readiness Ruler (RR);**

Non-Standardized Measures to be collected include:

Alternative depression treatments. We will ask participants whether they are currently using, or intend to use, any “alternative” treatments for depression such as BLT (including whether light box purchase was new or had existing), yoga, Tai Chi, mood-enhancing diets (e.g., Mediterranean Diet), exercise, omega-3 fatty acids, St John’s wort, and others.

Satisfaction and Feedback. At the 2-month follow-up assessment, we will ask participants in Arms 2 and 3 about their experience as a participant in this study.

Actigraphy

Following the baseline and 2-month follow-up assessments, participants will be mailed an actigraphy device to wear for 10 days or until the battery dies and then return in supplied postage-paid envelope. We will download/score actigraphy data for sleep and physical activity using ActiLife software, then reset the actigraphy device and reuse it again with additional participants.

Ecological Momentary Assessment (EMA)

Up to 4 days per week during the 9-week acute intervention phase (baseline to 2-month follow-up), and twice weekly thereafter to 6 months, all participants will be sent text and/or email links to a brief EMA REDCap survey about mood and sleep in the last 24 hours. For participants in Arms 2 and 3, the EMA survey will also include brief questions about BLT adherence.

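### The PHQ-9 outcome regression in the mediation model has no baseline terms, so if arm moves the mediator the indirect effect picks up the stable baseline sleep-depression association

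*Protocol*

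**What the plan says.** Protocol section 6a (Moderation and mediation) and the SAP section of the same name describe one mediation model. It is offered as an example and labelled exploratory, and the motivational-interviewing pathway is to follow a similar approach.

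- Mediator regression, Protocol: "we will regress post-acute treatment PSQI on baseline PSQI and a randomization condition indicator". The baseline mediator is included.
- Outcome regression, Protocol: "we will regress follow-up PHQ-9 at post-acute treatment PSQI and a randomization condition indicator". SAP: "we will regress follow-up PHQ-9 at post-acute treatment ISI and a randomization condition indicator". Neither lists baseline PHQ-9 or the baseline mediator, and no other section adds them.
- The indirect effect is the product of the two coefficients, with a bias-corrected bootstrap.

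Both texts frame mediation as acting through *changes* in the mediator, yet the outcome regression uses its post-treatment level.

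Baseline values exist for the survey measures: "All measures will be administered at the baseline assessment and all follow-up assessments unless otherwise indicated". Under Protocol section 4, randomisation follows the baseline assessment. Actigraphy differs: "Following the baseline and 2-month follow-up assessments, participants will be mailed an actigraphy device to wear for 10 days".

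The protocol's power section says the pilot is not powered for mediation. It also says the mediation analyses will be run as the full confirmatory trial would run them, to test the methods and give informative estimates. It states 80% power for paths of 0.43 and a detectable indirect effect of 0.19.

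**The concern.** Randomisation protects the effect of arm on the mediator (path a) and the total effect on PHQ-9. It does not protect the effect of the mediator on PHQ-9 (path b). People who start with worse sleep and worse depression tend to end with worse values of both. Without baseline terms, path b can be positive even if changing sleep does nothing to PHQ-9, and multiplying it by a real path a gives an indirect effect that is not there.

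Examining mediators is a stated secondary objective, and the pilot is meant to try out the method. Lack of power excuses an imprecise estimate but not a biased one, and this bias does not shrink as the sample grows.

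**Working it through.** **1. The plan's own figure.** 0.43 × 0.43 = 0.185, which rounds to the stated 0.19. Simulated bias-corrected bootstrap power at paths of 0.43 is 79.5% for 27 vs 27 (paths in residual-SD units) and about 95% for 54 vs 27. The stated 80% therefore fits a two-arm comparison in a model with no baseline confounding. The 0.19 serves below only as a yardstick.

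**2. Inputs.**
- From the documents: retained N = 81, randomised 1:1:1, hence 54 vs 27 for the pooled contrast; a = 0.43; autocorrelation 0.70, stated for the PHQ-9 growth model in both power sections and borrowed here as PHQ-9 stability.
- Assumed, because the documents are silent: baseline sleep-PHQ-9 correlation r0 = 0.2-0.5; sleep stability s = 0.3-0.7. PHQ-9 stability p = 0.5 is a milder alternative to 0.70.

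**3. Model with no true mediation.** All variables have unit variance within arm. M0 and Y0 are baseline sleep and PHQ-9, with correlation r0. M1 = s·M0 + a·arm + error; Y1 = p·Y0 + error, so true b = 0. Within arm, Cov(M1, Y1) = s·r0·p and Var(M1) = 1, so the planned regression estimates

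b = r0 × s × p, and indirect effect = a × b.

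| Case | r0 | s | p | false b | × 0.43 |
|---|---|---|---|---|---|
| Low | 0.20 | 0.3 | 0.70 | 0.042 | 0.018 |
| Middle | 0.35 | 0.5 | 0.70 | 0.1225 | 0.053 |
| High | 0.50 | 0.7 | 0.70 | 0.245 | 0.105 |
| Middle, milder p | 0.35 | 0.5 | 0.50 | 0.0875 | 0.038 |

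Simulation at N = 81 agrees: 0.088 and 0.038 for the last row, 0.246 and 0.107 for the high case. With both baseline terms added, b is about 0. If a = 0, the indirect effect averages about 0 even though b is biased.

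**4. Size against noise.** The standard error of planned b is about √(1/78) = 0.113. The false b is 0.0875/0.113 = 0.8 standard errors in the milder middle case and 0.1225/0.113 = 1.1 with p = 0.70. With a = 0.43 and true b = 0, the 95% interval excludes zero in 11% of simulated trials in the milder middle case (6% adjusted), and in 55% in the high case (5% adjusted).

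**5. Effect of the entry screens.** PHQ-9 must be 10 or more twice, in the health record and at screening. If the assumed r0 describes people before those screens, the milder middle case falls to b of 0.037-0.060 and an indirect effect of 0.016-0.026. This assumes a cut between 1 SD below the mean and the mean, and correlations of 0.6-0.8 between PHQ-9 occasions.

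**6. Precision of the adjusted model.** With both terms, SE(b) ≈ √[(1 − p²) / ((1 − s²) × 76)]:
- s = 0.3, p = 0.7: √(0.51/(0.91 × 76)) = 0.086
- s = p: √(1/76) = 0.115
- s = 0.7, p = 0.3: √(0.91/(0.51 × 76)) = 0.153

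In the last setting with r0 = 0.2, root mean squared error rises from 0.121 as planned to 0.153. Baseline PHQ-9 alone gives a standard error of 0.081-0.116. But if baseline sleep has its own effect of 0.1-0.2 SD on later PHQ-9 (r0 = 0.3, s = p = 0.5), planned b is 0.126-0.175, PHQ-9 alone leaves 0.048-0.094, and both terms leave 0.001-0.002.

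**The case against.** The strongest case against is about weight. The analysis is exploratory, the model is an example, the pilot is declared not powered for it, and no primary result or pilot decision rests on it. All of that stands. So does the point that the size depends on a correlation and a sleep stability that appear in neither document. Within plausible inputs the bias can be smaller than one standard error.

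It is also fair that adjustment is not always better at this sample size: with very stable sleep and unstable PHQ-9 it raises the error of b. At the plan's own 0.70 for PHQ-9 this largely disappears, because the formula in step 6 then gives 0.086-0.115 for s of 0.3-0.7, against about 0.11 as planned.

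The source sentence is ungrammatical. *At* may stand for *on*, or *on* may be missing after the words for the post-acute visit, which would place the outcome at month 2. Either reading leaves the outcome regression without baseline terms.

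A reader might infer more than the documents support:
- *That actigraphy mediation is invalid because the outcome precedes the second wear.* This holds only if the follow-up PHQ-9 is the month-2 one. SAP Rationale and research questions points to month 2, but Protocol section 6 (Assessments) separates the post-acute visit from follow-up at months 4 and 6.
- *That the mediation model cannot be run.* The SAP refers to "sleep (sleep diary and actigraphy, and ISI subjective sleep quality", while the protocol's list has "Pittsburgh Sleep Quality Index (PSQI); Reduced Version of the Morningness-Eveningness Questionnaire (rMEQ); Split Week Self-Assessment of Sleep Survey (SASS-Y" and no ISI. The protocol's PSQI version can be run, so this is a consistency error between documents.
- *That the full trial will inherit a known false-positive rate.* Neither document gives that trial's size, and it would have its own plan.

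**Conclusion.** The concern holds as a specification gap in an exploratory analysis that should be closed. As written, path b includes the stable baseline association between sleep and depression, and the indirect effect is biased whenever arm moves the mediator.

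On the stated assumptions, with PHQ-9 stability at 0.70, a sleep mediator with no effect would show an indirect effect of about 0.02-0.11, or 0.05 in the middle. That is roughly a quarter of the stated detectable 0.19 (0.053/0.19 = 0.28). With PHQ-9 stability 0.5 the middle value is 0.04, and the two entry screens may reduce it further. The top of the range needs the highest value of every input, so the 55% rate of false intervals is an upper-end result and should not be read as the expected one.

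The direction and mechanism are secure given a positive baseline correlation and some stability in both measures. The size is only illustrative. The primary PHQ-9 comparison and the arm effects on the mediators are not touched.

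**What to change.** In both Moderation and mediation sections:

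1. Write the outcome regression as PHQ-9 *on* the post-acute mediator and arm, and add baseline PHQ-9 and the baseline value of that mediator.
2. For actigraphy mediators, add baseline PHQ-9. Add the first-wear value only if it was worn before randomisation, since the device is mailed after the baseline assessment. Without a pre-randomisation wear the correction is partial.
3. State that baseline adjustment does not remove unmeasured or post-randomisation confounding of mediator and outcome.

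**Cost.** Wording and covariates already collected; no new data. At N = 81 the standard error of b with both terms is about 0.086-0.153, against about 0.11 as planned. Baseline PHQ-9 alone costs almost no precision but leaves some bias if baseline sleep affects later PHQ-9 directly; it could be reported as a sensitivity analysis.

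**Separate minor consistency edits.** Replace ISI with PSQI in the SAP. Reconcile the SAP's sleep diary with the protocol's SASS-Y; the diary could also be taken to mean the "brief EMA REDCap survey about mood and sleep in the last 24 hours". State which visit the follow-up PHQ-9 refers to. If it is month 2, note that the second actigraphy wear comes after the outcome.
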